4. PARTICIPANT ENTRY

4.1 PRE-RANDOMISATION EVALUATIONS

Study participants will be women needing IVF treatment for male factor infertility requiring intracytoplasmic sperm injection (ICSI), attending the IVF unit at Queen Charlottes and Chelsea Hospital, Imperial College Healthcare NHS Trust. Eligibility for the study will be determined at screening which will comprise a medical history, routine physical examination and basic investigations (including full blood count, urea and electrolytes, liver function tests, thyroid function tests, plasma glucose, lipid profile and electrocardiogram). Participants will be free to withdraw from the study at any time.

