The final dose of GnRH antagonist will be administered 24 hours prior to kisspeptin-54. Serum LH, FSH, oestradiol and progesterone will be measured immediately before, 12hrs and 36hrs after kisspeptin-54 injection, and at the time of egg retrieval in all women. Transvaginal ultrasound-directed oocyte retrieval (TVOR) will be carried out 36h following kisspeptin administration under intravenous anaesthesia (propofol). Intracytoplasmic sperm injection (ICSI) will be performed in all study cycles using sperm from the male partner to allow for assessment of oocyte maturation. All embryos will be graded at day 3 by an independent embryologist, blinded to doses of kisspeptin administered, using the British Fertility Society (BFS) and Association of Clinical Embryologist (ACE) embryo grading scheme for cleavage stage embryos, which describes embryos based on cell number, blastomere size and fragmentation.(30) If at day 3 at least 2 embryos have 6 or more cells, <20% difference in blastomere diameter and <50% fragmentation, they will be incubated until day 5 post oocyte retrieval in order that the strongest embryos can be identified for transfer. At Day 5, embryos will be graded for blastocyst expansion (1 to 6), inner cell mass (A to E) and trophectoderm (A to C).(30) At blastocyst stage, embryos which score at least 3 for blastocyst expansion and A or B for inner cell mass and trophectoderm will be classified as 'high quality embryos'. One or two embryos of highest quality during morphological assessment will be transferred to the uterine cavity 3-5 days following oocyte retrieval.

Assessment of Ovarian Hyperstimulation Syndrome (OHSS)

All women recruited to the study will be regarded as being at high risk of OHSS. Therefore women will be routinely screened for the development of early OHSS (assessed at embryo transfer 3-5days following oocyte retrieval) and late OHSS (assessed 11days following embryo transfer). Women will be screened by symptoms (abdominal pain, abdominal bloating, diarrhoea, nausea, vomiting, subjective reduction in urine output), blood analysis (hemoglobin, hematocrit, white cell count, liver function, renal function, coagulation profile) and ultrasound parameters (ovarian size, presence of free

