Baseline covariates which may need adjusting for include age, number of embryos transferred, number of high quality embryos transferred, cause of infertility and BMI.

-Rates of OHSS :

[figure not shown]
Covariates which may need to be adjusted for would include number of follicles >11mm on final ultrasound scan prior to trigger, serum AMH or antral follicle count, number of eggs collected, pretrigger oestradiol level.

List trial data as per CONSORT guidance:

Number of women screened, number who withdrew, number not eligible, number of women recruited and meeting inclusion criteria, but excluded prior to randomisation for complications requiring other IVF treatments prior to receiving kisspeptin eg hydrosalpinx.

We expect to recruit 62 women eligible for randomization (31 per group).

Example:

Tables to be generated following study completion:

Table 1:

Sort by column A	SINGLE	DOIUBLE	BOTH
N	31	31	62
Age (y) C			
Weight (kg) I			
Body mass index (kg/m²) J			
Antral Follicle Count (AFC) F			
Serum AMH* (pmol/L) E			
% with average cycle length \geq35 days D\geq35			
Cause of infertility: G			
PCOS [‡]			
Tubal defect**			
Male Factor [†]			
Mixed			
Idiopathic (unexplained)			
Number of follicles[¶] BF			
Number of Follicles \geq 11mm[¶]			
BK			
Number of Follicles \geq 14mm[¶]			
BN			

Table 1: Baseline characteristics of patients who received kisspeptin-54 trigger. Contains medians (lower quartile, upper quartile) for continuous variables and totals (percentages) for categorical variables.

* AMH = anti-Müllerian hormone

‡ Anovulation due to Polycystic Ovarian Syndrome.

** Blocked or removed Fallopian tubes.

† Infertility is due to a problem with male partner's fertility.

¶ On final ultrasound scan during controlled ovarian stimulation prior to kisspeptin-54 trigger administration.

Table 2:

	SINGLE (n = 31)	DOUBLE (n = 31)	BOTH (n = 62)
Number of Oocytes BZ			
Number of Mature (M2) Oocytes CA			
Oocyte Maturation Rate (%) * CD			
Oocyte Yield (%) † CG			
Proportion achieving ≥60% oocyte yield (%) CH			
Number of 2 pronuclei (2PN) zygotes CE			
Proportion with at Least 4 eggs collected (%) CB			
Fertilization rate (%) ‡ CF			
Number of patients with embryo transfer CN≥1			
Number of Cleaved embryos at day 3 post ICSI CI			
Number of Embryos at day 3 graded as ≥623 CJ			
Number of Patients with day 5 transfer % with CM=5			
Number of Embryos at day 5 CK			
Number of High quality blastocysts (≥3A/B) CL			

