Number of High quality blastocysts (>3A/B) transferred CO			
Number of Embryos suitable for freezing CV			
Biochemical Pregnancy rate per protocol (%) CP including those who did not have transfer as 0			
Biochemical Pregnancy rate per transfer (%) CP not including those who did not have transfer			
Clinical Pregnancy rate per protocol (%) CQ			

including those who did not have transfer as 0

Clinical Pregnancy rate per transfer (%) CQ
not including those who did not have transfer

Implantation rate (%) Ψ CU

Live Birth rate per protocol (%)

Table 2: IVF outcome measures following kisspeptin-54 trigger. Contains means (standard deviation) for continuous variables and totals (percentages of N) for categorical variables

* Oocyte Maturation Rate is the percentage of oocytes collected which were mature.

† Oocyte Yield is the percentage of mature oocytes collected from the number of follicles

≥ 14 mm in diameter on the final ultrasound scan prior to kisspeptin-54 trigger administration.

‡ Fertilization rate is the percentage of mature oocytes which fertilize following intracytoplasmic injection with sperm (ICSI).

Ψ Implantation rate is defined as the percentage of embryos transferred which implant on assessment by ultrasound at 6 weeks of gestation.

Table 3:

Kisspeptin-54 Dose	SINGLE		DOUBLE	BOTH	
	N	31	31		
At least 1 oocyte retrieved BZ\geq1					
At least 1 mature oocyte retrieved CA\geq1					
At least 1 2PN zygote formed \ddagger CE\geq1					
Segmentation Ψ					
Number of patients with embryo transfer CN\geq1					
Number of patients with day 5 transfer* % with CM=5					
High quality embryo transfer\dagger CO\geq1					
Biochemical pregnancy at 11 days CP					
Clinical pregnancy at 6 weeks CQ					
Miscarriage / Still Birth (PENDING)					
Live Birth (PENDING)					

Table 3: Summary of patient response following kisspeptin-54 triggering.

The number of patients completing each criterion is shown (% in brackets).

\ddagger 2PN is two pronuclear zygote assessed on day following oocyte retrieval

Ψ Segmentation refers to cryopreservation of all embryos and embryo transfer in a subsequent frozen cycle due to high risk of OHSS

* Embryo transfer on day 5

\dagger Transfer of at least one high quality embryo. High quality embryos were blastocyst embryos graded on day 5 as being at least 3A or B in quality (Gardner et al. 2000).

Table 4:

	Early OHSS By single vs double	Late OHSS By single by double
OHSS Symptomatology		

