Number of patients screened by OHSS symptoms		
At least 1 symptom potentially consistent with OHSS		
Number of patients requiring medical intervention or hospitalization for OHSS		
Sonographical Screening		
Number of patients screened with pelvic ultrasound		
Mean ovarian volume (mls)		
Increase in ovarian volume as proportion of baseline scan		
Max ovarian diameter (mm)		
Number of patients with maximum ovarian diameter >5cm		
Number of patients with maximum ovarian diameter >8cm		
Number of patients with pleural effusion		
Number of patients with free fluid in abdomen		
Number of patients with fluid in POD / adnexa		
Blood parameters		
Number of patients screened with Blood analysis		
Number of patients with Hematocrit >45%		
Number of patients with White Cell Count >15 x10 ⁹ /L		
Number of patients with ALT or AST >2xULN		
Number of patients with total protein >80 g/L		
Number of patient with creatinine >110 µmol/L		

Number of patients with OHSS ¥

Normal

Mild

Moderate

Severe

Critical

Table 4: OHSS in high risk women following kisspeptin-54 trigger

¥ Diagnosis of OHSS was performed by two experienced IVF physicians independent of the study team provided with blinded data according to the criteria of Golan et al. 1989 with updated categorization of severe and critical OHSS by Navot et al. 1992.(16,17)

POD, Pouch of douglas; ALT, Alanine transaminase; AST, Aspartate transaminase; ULN, Upper Limit of Normal.

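### SAP Table 4 summarises the OHSS blood markers only as counts above a cut-off, which discards information that any one-versus-two-dose comparison would need

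*SAP*

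**What the plan says.** The SAP randomises women to a second kisspeptin dose or saline and gives the size as "We expect to recruit 62 women eligible for randomization (31 per group").

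Its section on assessment of OHSS has all women screened twice: at embryo transfer, and 11 days after transfer. Each screen includes "blood analysis (hemoglobin, hematocrit, white cell count, liver function, renal function, coagulation profile").

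Table 4 reports these screens by arm, with column headings such as "Early OHSS By single vs double". Apart from the number of women who had bloods, all five blood rows are threshold counts:

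- "Number of patients with Hematocrit >45"%
- "Number of patients with White Cell Count >15" (×10⁹/L)
- "Number of patients with ALT or AST >2xULN"
- "Number of patients with total protein >80 g/L"
- creatinine above 110 µmol/L, in the same form.

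The ultrasound block of the same table is built differently. It gives mean ovarian volume, increase relative to the baseline scan and maximum diameter, and then adds counts above 5 cm and 8 cm.

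Protocol 4.1 lists "basic investigations (including full blood count, urea and electrolytes, liver function tests" at eligibility screening. The SAP makes no use of these as a baseline: its candidate covariates for OHSS rates are follicle number, AMH or antral follicle count, eggs collected and oestradiol.

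**The concern.** A cut-off count records only which side of a line each woman falls on. If the second dose raised haematocrit or white cell count across the whole arm, but most women stayed below the line, the two columns of Table 4 could look alike. The laboratory values that would show the shift are already in hand.

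This matters because avoiding OHSS is the protocol's main argument for kisspeptin, OHSS occurrence heads the SAP's list of secondary outcomes, and the randomised question is whether one dose or two should be given. Table 4 is the only printed summary of the blood results, and because it is split by arm, readers will compare arms from it.

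**Working it through.** **Inputs from the documents.** 31 women per arm (SAP). The SAP states no significance level for these rows, so I borrow the two-sided 5% from the LH calculation in Protocol section 9. The SAP gives no effect size, SD or power behind the 31 per group, so there is no figure of the plan's own to reproduce. The calculation in Protocol section 9 concerns LH by dose group and does not bear on this point.

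**Assumptions, not in the documents.** The marker is normal with equal SD in both arms. The true shift with the second dose is d = 0.5 or 0.7 SD. The cut-off lies c = 1, 1.5, 2 or 2.5 SD above the single-dose mean. All 31 women per arm have data.

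**Step 1: share above the cut-off.** Single dose: p1 = 1 − Φ(c). Double dose: p2 = 1 − Φ(c − d). For c = 2 and d = 0.7, p1 = 1 − Φ(2) = 2.3% and p2 = 1 − Φ(1.3) = 9.7%. Expected counts are 31 × 0.023 = 0.7 and 31 × 0.097 = 3.0 women.

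**Step 2: power of the count comparison.** Sum the two binomial probabilities (31, p1) and (31, p2) over all tables with Fisher p ≤ 0.05.

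| Cut-off above single-dose mean | p1 | p2, d = 0.5 | Power, d = 0.5 | p2, d = 0.7 | Power, d = 0.7 |
|---|---|---|---|---|---|
| 1 SD | 15.9% | 30.9% | 20% | 38.2% | 42% |
| 1.5 SD | 6.7% | 15.9% | 9% | 21.2% | 23% |
| 2 SD | 2.3% | 6.7% | 0.8% | 9.7% | 3.9% |
| 2.5 SD | 0.6% | 2.3% | 0.01% | 3.6% | 0.06% |

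For scale, 0 against 5 women above a cut-off gives p = 0.053. It takes 0 against 6 (p = 0.024) or 1 against 8 to pass 5%.

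**Step 3: power of the comparison of means.** Two-sample t test with 60 degrees of freedom and noncentrality d × √(31/2) = 3.94d. For d = 0.5 this is 1.97 and power is 49%. For d = 0.7 it is 2.76 and power is 77%. The shift detectable with 80% power is 0.72 SD.

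**Step 4: adding a baseline.** With correlation r between screening and follow-up values, the residual SD is multiplied by √(1 − r²). At d = 0.7, r = 0.3 gives 81% and r = 0.5 gives 88%. At d = 0.5, the same values give 53% and 61%. No document supports a value of r, so the main comparison is the unadjusted one in step 3.

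**The case against.** **Table 4 is a descriptive shell.** It stands among example tables to be produced after the study, names no test for the blood rows, and blood markers are not named outcomes. This stands. A reader might infer that the plan will declare no difference in blood parameters; nothing in the documents plans that conclusion. The power figures describe what a comparison made from these rows could show, not a test that the SAP specifies.

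**Other data carry part of the safety comparison.** Two external clinicians, working from blinded data, grade OHSS from symptoms, bloods and ultrasound, and Table 4 reports that grade and the continuous ovarian measures. This stands too. A reader might add that graded OHSS will yield too few events to help, but no document gives an OHSS rate after kisspeptin. The protocol's general IVF rates, about 1 in 3 for mild and 1 in 10 for moderate or severe, would give 62/3 ≈ 21 and 62/10 ≈ 6 women.

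**The sizes rest on assumptions.** It is tempting to say that the count rows have almost no power. That holds only when few women exceed a cut-off; at 1 SD the power is 20% to 42%. Nor are means a cure: at 0.5 SD they have only 49%.

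**The data may be incomplete and the baseline weak.** Both screens are timed from embryo transfer, while Table 3 allows for freezing all embryos because of OHSS risk, so 31 per arm with bloods is not assured and missingness may be related to OHSS. The screening bloods carry no date relative to stimulation, and total protein is not named among them. These points limit the adjusted analysis but do not favour counts over means.

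**More comparisons bring false positives.** Five markers at two screens make ten. If independent and each tested at 5%, the chance of at least one false positive is 1 − 0.95¹⁰ = 40%. This is why they should be labelled supportive.

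A figure under the SAP's heading on OHSS rates is not visible in the text available, so its content cannot be judged. The blood rows of Table 4 are legible as they stand.

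**Conclusion.** The concern holds as a cheap improvement to a supporting safety summary. All five blood results are reduced to counts, although the underlying values are measured and the same table treats ovarian size continuously. Under the stated assumptions the means are more informative at every cut-off examined: 49% to 77% power, against 20% to 42% for a cut-off at 1 SD and under 5% at 2 SD or more. The ordering is secure within this normal-shift model. The sizes depend on the assumed shift, the distance of each cut-off from the single-dose mean and full data on 31 per arm, none of which the documents settle. The finding does not touch the primary outcome or the OHSS grading, and it does not show that the trial would miss a difference in OHSS.

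**What to change.** Keep the cut-off counts in Table 4 as safety flags and make these additions to the SAP:

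- For haematocrit, white cell count, ALT/AST, total protein and creatinine, give the mean (SD) or median (quartiles) by arm at each screen, with the number of women who have data.
- Give the between-arm difference with a 95% CI, on the log scale for ALT/AST.
- Adjust for the woman's own screening value where that analyte was measured. Protocol 4.1 covers the full blood count, urea and electrolytes and liver function tests; where no screening value exists, as may be so for total protein, report the difference unadjusted.
- Label these comparisons supportive, with no multiplicity claim, and read the estimates and intervals rather than p-values.

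The cost is a paragraph of SAP text, some added rows and columns, and about ten extra secondary estimates. No new samples or visits are needed.
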